5.2.3. Exploratory Objectives

The exploratory objectives of this study are:

- to evaluate blood, CTCs, and tumor tissue pre- and post-therapy for biomarkers related to pathways associated with STS, the MOA of olaratumab, cancer-related conditions, and/or immune cells/immune and tumor microenvironment functioning within the disease state and/or cancer-related conditions.
- to assess the relationship between biomarker expression at baseline, and change from baseline, and clinical outcomes.

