6.2. Summary of Study Design

Study JGDM is an open-label, single-arm, multicenter, multicountry Phase 1b study to enumerate whole blood CTCs and to characterize PDGFR α and PDGFR β and canonical ligands (*PDGF-A, B, C* and *D*) expression changes pre- and post-olaratumab monotherapy in tumor tissue in patients with potentially resectable STS.

Patients are to be treated with 20 mg/kg of olaratumab on Day 1 and Day 8 of Cycle 1, followed by up to 6 cycles (Cycle 2 – Cycle 7) of combination therapy with olaratumab plus doxorubicin. For Cycle 2, olaratumab is to be dosed at 20 mg/kg on Day 1 and Day 8 and doxorubicin is to be dosed at 75 mg/m² on Day 1. For Cycle 3 – Cycle 7, olaratumab is to be dosed at 15 mg/kg on Day 1 and Day 8 and doxorubicin is to be dosed at 75 mg/m² on Day 1. Each cycle of treatment is defined as an interval of 21 days. Approximately 35 patients are to be enrolled.

Starting with the first cycle of combination therapy (Cycle 2), the use of dexrazoxane (in a 10:1 ratio vs. doxorubicin dose) to mitigate cardiotoxicity during treatment with doxorubicin is allowed at the investigator's discretion and is recommended for all patients receiving 5 or more cycles of doxorubicin.

[figure not shown]
Tissue biopsies are required pre- and posttreatment with olaratumab monotherapy. The pretreatment tissue biopsy is to be performed within the screening period. The posttreatment tissue biopsy is to be performed after completion of the lead-in cycle of olaratumab monotherapy and prior to the initiation of combination therapy in Cycle 2. An optional third tissue biopsy (or tissue from a posttherapy surgical resection specimen) may be performed at the end of the patient's study treatment. If clinically feasible, the tissue biopsies should be taken from the same primary tumor lesion. If the patient has an additional surgical resection, tissue from this procedure is requested. Refer to Section 8.2.3.2 for details on tissue biopsies.

Whole blood samples for CTC analyses are to be collected predose at Cycle 1 Day 1 (C1D1), at Cycle 1 Day 8 (C1D8), at Cycle 2 Day 1 (C2D1), at Cycle 2 Day 8 (C2D8), at Cycle 3 Day 1 (C3D1), and at the end of the patient's study treatment or at the time of surgical resection. Refer to Section 8.2.3.1 for details on blood samples.

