7.6.1. Evaluable Patients

Evaluable patients are those with adequate biomarker samples who have a baseline (pre-monotherapy) and at least 1 postbaseline measurement. Patients who withdraw from the study before receiving study drug will be replaced and will not be included in the safety or primary objective assessments. Safety analyses will be conducted on all patients who have received at least 1 dose of study drug.

If the patient is noncompliant during olaratumab monotherapy (Cycle 1) and does not undergo the post-olaratumab monotherapy biopsy or the C1D1 pre-dose and C2D1 predose whole blood sample collection due to reasons other than drug-related toxicity, he or she will be considered nonevaluable for the primary objective. These patients may be replaced to ensure that 35

patients complete the pre-treatment tissue biopsy, the C1D1 pre-dose whole blood sample collection, 1 cycle of olaratumab monotherapy, and the post-olaratumab monotherapy biopsy, and the associated C2D1 predose whole blood sample collection.

8. Safety, Pharmacokinetic, Pharmacodynamic, and Efficacy Data Collection

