10.1.2. Analysis Populations

Efficacy analysis: the efficacy analysis will be performed on the intent-to-treat (ITT) population, which includes all enrolled patients. The ITT population will be included in overall patient listings, in summary tables of patient demographics and disease characteristics, in the list of treatment discontinuation after enrollment, and in the analysis of efficacy.

Safety analysis: all enrolled patients who receive any quantity of IP, regardless of their eligibility for the study, will be included in the safety analysis. Safety evaluation will be performed based on the actual therapy a patient has received.

Biomarker analysis: the biomarker evaluable 1 (BE1) population will include all ITT patients with evaluable samples at both baseline and post-olatumab monotherapy. The BE1 population will be used in the biomarker analyses for the primary objective and exploratory objectives. The biomarker evaluable 2 (BE2) population will include all ITT population with evaluable samples at both baseline and post-combination (olatumab plus doxorubicin) therapy, and will be used in the biomarker analyses for the exploratory objectives.

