			Olaratumab Monotherapy		Combination Therapy Olaratumab + Doxorubicin		Olaratumab Monotherapy		Combination Therapy Olaratumab + Doxorubicin		
			1		2-7		1		2-7		
			1 ^{a,b}	8 ^a	1 ^{a,b}	8 ^a	1 ^{a,b}	8 ^a	1 ^{a,b}	8 ^a	
	8.2.5 Attachment 4	Immunogenicity Samples	See Attachment 4 for specific time points				Whole blood samples collected. If a patient experiences an IRR to olaratumab, blood samples for immunogenicity and PK analysis will be taken at the following time points: (1) as soon as possible after the onset of the IRR, (2) at the resolution of the IRR, and (3) 30 (± 3 days) days after onset of the IRR event.				
Lab/ Diagnostic Tests	8.2.4	Pharmacogenetic Whole Blood Sample for DNA storage	X							Whole blood sample collected. It is highly recommended to draw the whole blood sample prior to the first dose (C1D1 at predose); however, it can be collected later during the study if necessary.	
	8.2.3 Attachment 4	Plasma sample for exploratory biomarkers	X		See Attachment 4 for specific time points					Plasma sample collected. C1D1 at predose, C2D1 (combination therapy pre-dose) and at the end of the patient's study treatment. See Section 8.2.3.1 and Attachment 4 for details and specific time points.	
	8.2.3 Attachment 4	Serum sample for exploratory biomarkers	X		See Attachment 4 for specific time points					Serum sample collected. C1D1 at predose, C2D1 (combination therapy pre-dose) and at the end of the patient's study treatment. See Section 8.2.3.1 and Attachment 4 for details and specific time points.	
	8.2.3 Attachment 4	Mandatory Whole Blood Collection for Circulating Tumor Cells	X		See Attachment 4 for specific time points					Collect mandatory peripheral whole blood samples predose at C1D1, C1D8, C2D1, C2D8, and C3D1, and at end of the patient's study treatment or at the time of surgical resection. See Section 8.2.3.1 and Attachment 4 for details.	
	8.2.3	Mandatory Tumor Tissue				X				Mandatory tumor tissue must be collected up to 3 days prior to the first dose of C2D1. When submitting a specimen from a tumor resection after or during combination therapy, sites should examine samples to determine adequacy of tumor tissue using their local laboratory procedures. If additional tumor biopsies are collected as part of clinical care, they should be submitted, along with pathology reports, for further analysis. See Section 8.2.3.2 for details.	

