postbaseline tumor response assessments for any reason are considered non-responders and are included in the denominator when calculating the response rate.

Progression-free survival (PFS) is defined as the time from the date of first study dose to the first date of radiologic disease progression or death due to any cause. [Table JGDM.5.1](#) defines the rules of censoring to be applied to PFS.

3-month Progression-free survival (PFS) is defined as the 3-month PFS rate as estimated using Kaplan-Meier methods. PFS is as defined above.

Rate of Resection is defined to be the percentage of patients whose tumors are determined to be resectable divided by the total number of patients. The evaluation of resectability of a tumor is determined by the surgeon in consultation with the multi-disciplinary team, and depends on the tumor stage and the patient's co-morbidity. The primary aim of surgery is to completely excise the tumor with a margin of normal tissue.

Table JGDM.5.1. Censoring Rule of PFS Primary Analysis

Situation	Event / Censor ^d	Date of Event or Censor ^e
Tumor progression^a or death	Event	Earliest date of PD or death
No tumor progression and no death	Censored	Date of last adequate radiological assessment or date of first study dose
unless		
No baseline radiological tumor assessment available	Censored	Date of first study dose
No adequate^b postbaseline radiological tumor assessment available and death reported after 2 scan intervals ^c following first study dose	Censored	Date of first study dose
New anticancer treatment (including surgery) started and no tumor progression or death within 14 days	Censored	Date of adequate radiological assessment prior to (start of new therapy +14 days) or date of first study dose (whichever is later)
Tumor progression or death documented immediately after 2 or more consecutive missing scan intervals following last adequate radiological tumor assessment or first study dose (whichever is later)	Censored	Date of last adequate radiological assessment prior to the missing assessment or date of first study dose

Abbreviations: CR = complete response; PD = progressive disease; PFS = progression free survival; PR = partial response; SD = stable disease.

- a Symptomatic deteriorations (that is, symptomatic progressions, which are not radiologically confirmed) will not be considered as disease progressions.

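### Relating baseline expression to clinical outcome needs only the baseline sample, but the plan assigns it to populations that also require a later sample

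*Protocol*

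**What the plan says.** Protocol 5.2.3 and SAP 4.3 set as an exploratory objective "to assess the relationship between biomarker expression at baseline, and change from baseline, and clinical outcomes". This contains two questions: one about the baseline value, one about the change.

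Protocol 10.1.2 defines two biomarker populations, and SAP Table JGDM.5.2 repeats them.

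- BE1: the "population will include all ITT patients with evaluable samples at both baseline and post-olatumab monotherapy". Its use: "The BE1 population will be used in the biomarker analyses for the primary objective and exploratory objectives".
- BE2: patients with "evaluable samples at both baseline and post-combination (olatumab plus doxorubicin) therapy, and will be used in the biomarker analyses for the exploratory objectives".

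The general evaluability rule in protocol 7.6.1 points the same way: "Evaluable patients are those with adequate biomarker samples who have a baseline (pre-monotherapy) and at least 1 postbaseline measurement". The ITT population is assigned to listings, demographics, disease characteristics, treatment discontinuation and efficacy, but not to biomarker analyses. Neither document defines a population that needs only an evaluable baseline sample.

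**The concern.** For the baseline half of the objective, the predictor is complete once the pretreatment sample has been read. Requiring a second sample makes membership depend on what happens after treatment starts. Patients who die, deteriorate, withdraw, decline the second biopsy or give an inadequate one drop out of the analysis, although their baseline value is known and their outcome is handled in the efficacy analysis.

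Two things are at stake. One is precision, in a study of about 35 evaluable patients where each failure carries information. The other is selection: if missing the later sample is related to both the marker and the outcome, the estimated association changes. Replacement under protocol 7.6.1 does not remove this, because it fills the places with patients who did reach the second sample.

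**Working it through.** The plan gives no figure on this point. Its one sample-size figure, the 95% CI for 17 of 35, reproduces by the exact method (31.4% to 66.0%, stated as 31% to 66%). It concerns the primary hit rate and plays no part below.

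**1. When membership is decided.** Attachment 1 states: "Mandatory tumor tissue must be collected up to 3 days prior to the first dose of C2D1". With 21-day cycles, C2D1 is Day 22, so the BE1 tissue sample falls on about Days 19 to 22. The first scheduled scan is 6 weeks from enrollment, up to 7 days early, so about Days 35 to 42. PFS starts earlier than either, at enrollment (protocol 10.6) or first dose (SAP 5.3.5). Losses before the BE1 sample are therefore deaths, unscheduled or clinical progression, toxicity, withdrawal and inadequate biopsies, not progression found on a scheduled scan.

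For BE2 tissue the sample comes much later and is voluntary: "An optional third tissue biopsy (or tissue from a posttherapy surgical resection specimen) may be performed at the end". Membership can then depend on being resected, and resectability is itself a secondary endpoint.

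**2. What happens to the outcome of a patient left out.**
- Response endpoints: under SAP 5.3.5, patients without "postbaseline tumor response assessments for any reason are considered non-responders and are included in the denominator". Such a patient counts as a failure in the efficacy analysis.
- PFS: with no adequate postbaseline scan, SAP Table JGDM.5.1 censors a death only if it comes after two scan intervals, so an early death is an event. A patient who stops treatment for toxicity is still imaged every 6 weeks (protocol 6.2).
- A patient who leaves the study with no postbaseline scan and no recorded death is censored at time zero and adds nothing to PFS under either choice of population.

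**3. Precision, if loss is unrelated to outcome.** The standard error scales with 1/√n. The numbers treated and kept are assumed.
- 35 of 40 kept: √(40/35) = 1.069, about 7% larger.
- 20 of 40 kept, as might occur for BE2 tissue: √(40/20) = 1.414, about 41% larger.

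**4. Bias, if the patients lost are early failures.** All rates here are assumed. Take a marker read as positive or negative, which is how SAP 5.3.2 reports both receptors, with 20 low and 20 high patients. Let f be the true failure probability (30% low, 50% high) and e the part of it that occurs before the later sample. Among those kept:

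- failure rate r = (f − e)/(1 − e)
- odds r/(1 − r) = (f − e)/(1 − f)
- so OR(kept) = OR(all) × (1 − e_high/f_high)/(1 − e_low/f_low)

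OR(all) = (0.50/0.50)/(0.30/0.70) = 2.33.

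| Early loss, low / high | Kept of 40 | Failure among kept, low / high | Risk difference (points) | OR |
|---|---|---|---|---|
| none | 40 | 30.0% / 50.0% | 20.0 | 2.33 |
| 5% / 5% | 38 | 26.3% / 47.4% | 21.1 | 2.52 |
| 5% / 10% | 37 | 26.3% / 44.4% | 18.1 | 2.24 |
| 5% / 15% | 36 | 26.3% / 41.2% | 14.9 | 1.96 |
| 5% / 20% | 35 | 26.3% / 37.5% | 11.2 | 1.68 |
| 15% / 30% (BE2-like) | 31 | 17.6% / 28.6% | 10.9 | 1.87 |
| 20% / 40% (BE2-like) | 28 | 12.5% / 16.7% | 4.2 | 1.40 |

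The last formula settles the direction. The odds ratio is unchanged when the same share of failures is lost early in both marker groups. It moves toward 1 when the larger share is lost in the high group, and away from 1 when the larger share is lost in the low group. In the 5% / 5% row those shares are 5/30 = 16.7% (low) and 5/50 = 10% (high), so the odds ratio rises.

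**The case against.** The case for leaving the text alone has several parts.

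- **Early losses may be few.** Patients have potentially resectable disease, ECOG 0 to 1 and an expected survival of at least 3 months. Protocol 5.4 describes single-agent olaratumab as well tolerated. The BE1 sample is due before the first scheduled scan. This stands: the BE1 effect may be small, and the loss rates in the table have no support in the documents. Declining a second biopsy is also not in itself an outcome failure.
- **The objective is exploratory and the analyses are mainly descriptive.** This stands and limits the weight of the point.
- **The SAP leaves room.** SAP 5.9 allows a separate biomarker analysis plan if one is thought necessary, and SAP 5.2 allows exploratory analyses not described. A reader might infer that the plan forbids a baseline-only analysis or throws the samples away; it does neither. But an optional later document does not alter the assignment that both current documents make.
- **BE2 for blood may not depend on the optional tissue.** The C2D8 and C3D1 draws for CTCs follow the first combination dose and appear under mandatory collection in Attachment 1. The documents do not say whether these count as post-combination samples, nor which exploratory analysis uses BE1 and which BE2. The heavier BE2 loss is therefore a statement about tissue only.
- **Toxicity is not a settled exclusion.** The nonevaluable rule excepts drug-related toxicity, while the BE1 definition still requires both samples. How these patients are classed is ambiguous.

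A reader might also take the earlier trial's finding in protocol 5.1, that receptor expression did not predict survival, as making baseline prediction a main purpose here. The protocol uses that finding to justify paired sampling of the same lesion, and the outcome there was overall survival.

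**Conclusion.** The mismatch is real and is visible in both documents: one half of one exploratory objective is tied to populations that select on a post-baseline event the analysis does not need. The certain cost is some precision. Bias arises only if the loss is related to both marker and outcome, and its direction is open.

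A reader might infer that the association is necessarily pulled toward the null. The documents do not support that, and the arithmetic shows it unchanged or strengthened under other loss patterns. The odds ratios above are illustrations under assumed failure and loss rates, not estimates for this trial.

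A reader might also infer that the primary analysis is compromised. It is not: pre-to-post change requires both samples, so BE1 is the right population for it and for the change half of this objective. The point is modest in weight, larger for BE2 tissue than for BE1, and worth correcting because the correction is almost free.

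**What to change.** In protocol 10.1.2 and SAP Table JGDM.5.2, add a baseline-evaluable population: all treated patients with an evaluable baseline sample for the marker concerned, regardless of later samples and whether or not the patient was replaced. Use it for baseline expression against PFS, ORR, DCR and resectability. Keep BE1 and BE2 for analyses of change from baseline. Report how many patients are in the baseline-evaluable population but not in BE1 or BE2, with reasons, so that readers can judge the selection in the change analyses.

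The cost is one added population row in each document and the matching analysis specification. No further samples, visits or patients are needed.

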10.2. Patient Disposition

All patient discontinuations will be documented, and the extent of each patient's participation in the study will be reported. If known, a reason for their discontinuation will be given.

10.3. Patient Characteristics

Patient characteristics will include a summary of the following:

- Patient demographics including age, sex, screening height and weight, and screening body mass index will be reported
- Baseline disease characteristics
- Historical diagnoses
- Pre-existing conditions
- Prior disease-related therapies
- Concomitant medications
- Tissue histology grouped as leiomyosarcoma (LMS) or non-LMS.

Other patient characteristics will be summarized as deemed appropriate.

10.4. Safety Analyses

All patients who receive at least 1 dose of study drug will be evaluated for safety and toxicity.

The safety and tolerability of study drug is determined by reported AEs, physical examinations, laboratory tests, ECGs, dose adjustments, and results from ECHO/MUGA scans.

All patients will be assessed regularly for potential occurrence of AEs from the time that the patient provides informed consent until 30 days after the last dose of study therapy. Adverse events will be summarized by MedDRA System Organ Class and preferred term, classified from verbatim terms. The incidence and percentage of patients with at least 1 occurrence of a

preferred term will be included, according to the most severe NCI-CTCAE Version 4.0 grade. The number of AEs reported per MedDRA preferred term will also be summarized. Causality (relationship to study drug) will be summarized separately. Duration of AE will be determined and included in listings along with action taken and outcome.

Laboratory results will be classified according to NCI-CTCAE Version 4.0. Incidence of laboratory abnormalities will be summarized; laboratory results not corresponding to an NCI-CTCAE Version 4.0 term will not be graded. Laboratory toxicity shifts from baseline to worst grade will also be provided.

The results from physical examination and vital sign measurement will be tabulated. Descriptive statistics will be provided as appropriate. Electrocardiogram and ECHO/MUGA evaluation will be listed.

10.5. Biomarker Analyses

Primary analysis:

All patients in the BE1 population will be evaluated for:

- CTC enumeration in whole blood
- PDGFR α , PDGFR β , and canonical ligand (*PDGF-A, B, C, and D*) expression in tumor tissue.

The percent change from baseline for post-olatumab monotherapy in biomarker expressions will be provided for each patient and summarized for all qualified patients. Summary of number and frequency of patients with at least 30% reduction in change from baseline PDGFR α expression will also be provided. For patients with an observed value of 0 for baseline expression or both baseline and post-olatumab monotherapy expressions, a value of 0.1 will be used.

10.6. Efficacy

The following secondary efficacy endpoints will be measured:

Progression-free survival (PFS): is defined as the time from enrollment until the first radiographic documentation of objective progression as defined by RECIST (v1.1) ([Attachment 8](#)), or death from any cause. Patients who die without a reported prior progression will be considered to have progressed on the day of their death. Patients who did not progress or who are lost to follow-up will be censored at the day of their last radiographic tumor assessment. If no baseline or postbaseline radiologic assessment is available, the patient will be censored at the date of enrollment. If death or PD occurs after 2 or more consecutive missing radiographic visits, censoring will occur at the date of the last radiographic visit prior to the missed visits. The use of a new anticancer therapy or the performance of a surgical resection prior to the occurrence of PD will result in censoring at the date of last radiographic assessment prior to initiation of new therapy or surgical resection.

3-month PFS: estimated as the total number of patients who did not progress 3 months after enrollment divided by the total number of patients.

Overall response rate (ORR): estimated as the total number of CRs, complete responses unconfirmed (CRus), and PRs divided by the total number of patients.

Disease control rate (DCR): is computed as the total number of patients with the best overall response of CR, CRu, PR, or SD divided by the total number of patients.

Rate of Resectability: is defined as the total number of patients who are resectable (see definition of resectability in Section 4) divided by the total number of patients.

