enroll	Patients who are enrolled in the trial are those who have been assigned to a treatment and have received at least 1 dose of study treatment.
enter	Patients who are entered in the trial are those who have signed the informed consent form directly or through their legally acceptable representatives.
ERB/IRB	ethical review board/institutional review board: /A board or committee (institutional, regional, or national) composed of medical and nonmedical members whose responsibility is to verify that the safety, welfare, and human rights of the patients participating in a clinical study are protected.
GCP	good clinical practice
G-CSF	granulocyte colony stimulating factor
GIST	gastrointestinal stromal tumors
HR	hazard ratio
IB	Investigator's Brochure
ICF	informed consent form
ICH	International Conference on Harmonisation
IG	immunogenicity
IgG1	immunoglobulin G, subclass 1
IHC	immunohistochemistry
informed consent	A process by which a patient voluntarily confirms his or her willingness to participate in a particular trial, after having been informed of all aspects of the trial that are relevant to the patient's decision to participate. Informed consent is documented by means of a written, signed and dated informed consent form.
interim analysis	An analysis of clinical study data that is conducted before the final reporting database is authorized for datalock.
IRR	infusion-related reaction

investigational product (IP)	A pharmaceutical form of an active substance or placebo being tested or used as a reference in a clinical trial. Investigational product includes a product with a marketing authorization when: 
 1. used or assembled (formulated or packaged) in a way different from the authorized form 2. used for an unauthorized indication or 3. used to gain further information about the authorized form
investigator	A person responsible for the conduct of the clinical study at a study site. If a study is conducted by a team of individuals at a study site, the investigator is the responsible leader of the team and may be called the principal investigator.
ITT	intent-to-treat
IV	intravenous(ly)
IWRS	Interactive Web Response System
legal representative	An individual, judicial, or other body authorized under applicable law to consent on behalf of a prospective patient, to the patient's participation in the clinical study.

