7.3. Method of Assignment to Treatment

Patients who meet all criteria for enrollment will be assigned to receive treatment. After the patient signs the ICF, the site will register the patient in the Interactive Web Response System (IWRS), which is web-based and accessible 24 hours a day. The IWRS registration consists of assigning the patient a unique study identification number. Once the patient is registered through the IWRS, he/she is considered to be enrolled in the study.

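### Protocol 10.6 estimates 3-month PFS as a crude proportion with no rule for early censoring, while the SAP uses Kaplan-Meier; other PFS rules also differ or are unclear.

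*Protocol*

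**What the plan says.** **3-month PFS.** Protocol 10.6 says it is "estimated as the total number of patients who did not progress 3 months after enrollment divided by the total number of patients". SAP 5.3.5 says it "is defined as the 3-month PFS rate as estimated using Kaplan-Meier methods". Protocol 10.1 plans Kaplan-Meier curves for all time-to-event endpoints, with rates at time points and 95% CIs.

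**Start of the clock.** In Protocol 10.6, PFS "is defined as the time from enrollment until the first radiographic documentation of objective progression" or death. In SAP 5.3.5 it is the "time from the date of first study dose to the first date of radiologic disease progression" or death. Enrollment itself has two meanings. Protocol 7.3 says "Once the patient is registered through the IWRS, he/she is considered to be enrolled in the study", while Protocol Section 4 reserves the term for patients who "have been assigned to a treatment and have received at least 1 dose of study treatment".

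**Death without a scan.** Protocol 10.6 counts a patient who dies without reported progression as progressing on the day of death. Two sentences later it says "If no baseline or postbaseline radiologic assessment is available, the patient will be censored at the date of enrollment", with no mention of death. SAP Table JGDM.5.1 censors a death with no adequate postbaseline scan only when it comes after 2 scan intervals.

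**New therapy or surgery.** Protocol 10.6 censors at the last scan before either one. SAP Table JGDM.5.1 keeps progression or death within 14 days afterwards as an event, and otherwise censors at the "Date of adequate radiological assessment prior to (start of new therapy +14 days").

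Neither document says which definition governs. The SAP revision history mentions no change to PFS.

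**The concern.** PFS and 3-month PFS are named secondary endpoints in both documents, yet a programmer working from Protocol 10.6 and one working from SAP 5.3.5 could report different 3-month figures from the same data.

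The estimator is the main issue. A crude proportion over all patients is sound only if everyone's status at 3 months is known. Here patients enter because their tumor may be resectable. Resection ends study treatment and censors PFS, and Protocol 6.2 stops progression imaging after resection. A patient resected at week 8 therefore has unknown 3-month status. Read literally, the protocol formula counts that patient as not having progressed, so the figure is too high. The other differences are smaller, but left open they allow the choice of rule to be made after the data are seen.

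**Working it through.** The documents state no planned value for PFS or 3-month PFS, so there is no figure to reproduce. The check applies both rules to the same assumed data.

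**1. Bias of the crude rule**

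Inputs:
- Median PFS of 4.1 and 6.6 months, the two Study JGDG arms in Protocol 5.1. That trial enrolled advanced disease, so these are stand-ins.
- Exponential PFS (assumed).
- A share r of patients assigned a censoring time C uniform on 0 to 3 months, independent of progression (assumed; r = 20% and 40%).

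Formulas, with x = 3 ln 2 / median:
- True rate: S(3) = exp(−x)
- Chance that a patient with a censoring time shows no progression before it: E = (1 − S(3)) / x
- Crude rate, literal reading: (1 − r) S(3) + r E
- Bias: r (E − S(3))

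| | Median 4.1 | Median 6.6 |
|---|---|---|
| x | 0.507 | 0.315 |
| S(3) | 60.2% | 73.0% |
| E | 78.4% | 85.8% |
| Crude rate, r = 20% | 63.9% | 75.5% |
| Bias, r = 20% | 3.6 points | 2.6 points |
| Crude rate, r = 40% | 67.5% | 78.1% |
| Bias, r = 40% | 7.3 points | 5.1 points |

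Biases come from unrounded values. Some patients progress before their assigned censoring time, so at r = 20% only 0.20 × 78.4% = 15.7% and 0.20 × 85.8% = 17.2% are observed as censored. Kaplan-Meier is consistent for S(3) under these assumptions.

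**2. The same point with 35 patients and 6-weekly scans**

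Assume 5 progressions on day 42, 5 on day 84, and c patients resected after the day-42 scan and censored there. Three months is 3 × 30.4375 = 91.3 days.

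- Crude, literal: 25/35 = 71.4% for every c.
- Kaplan-Meier: (30/35) × (1 − 5/(30 − c)).

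| c | Crude | Kaplan-Meier | Gap (points) |
|---|---|---|---|
| 0 | 71.4% | 71.4% | 0 |
| 5 | 71.4% | 68.6% | 2.9 |
| 10 | 71.4% | 64.3% | 7.1 |
| 15 | 71.4% | 57.1% | 14.3 |

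**3. The other differences**

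- *Start date.* Protocol Attachment 1 aims for first dose within 3 days of enrollment where possible. The shift is at most 3/30.4375 = 0.10 month when that target is met, and zero if enrolled means dosed.
- *14-day window.* Take c = 5 and let 1, 2 or 3 of the resected patients have an event on day 60, within 14 days of surgery. The SAP rule gives Kaplan-Meier rates of 65.9%, 63.5% and 61.2%. The protocol rule gives 68.6% each time. The gap is 2.6 to 7.4 points.
- *Death before any postbaseline scan.* Two scan intervals under the note to SAP Table JGDM.5.1 are 2 × 42 + 14 = 98 days. Take c = 5 and add 1, 2 or 3 deaths on day 30. As events they give 65.6%, 62.6% and 59.6%. Censored at enrollment they give 67.5%, 66.4% and 65.2%. The gap of 1.9 to 5.6 points arises only if the protocol's no-scan sentence overrides its death sentence.

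All event counts in parts 2 and 3 are assumed. They show direction and rough size and are not forecasts.

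**The case against.** The strongest reply is that little depends on this. SAP 5.3.5 says the study was not designed to assess efficacy, the analyses are descriptive, and no test, sample size or stopping decision uses PFS. At 20% assigned censoring the bias of 2.6 to 3.6 points is small beside a 95% half-width of about 15 to 16 points at N = 35 (1.96 × √(S(1 − S)/35)). Kaplan-Meier is not immune either: resection plausibly depends on how the tumor is doing, so the censoring may be informative. All of this stands. It limits the severity but does not reconcile the two estimators.

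Some stronger readings are tempting but not supported:

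- *The protocol drops the earliest deaths.* The no-scan sentence follows the one on patients who did not progress or were lost to follow-up, and can be read as fixing a censoring date only for patients without an event. The wording is ambiguous; it does not clearly remove deaths.
- *The crude rate could be far too low.* Counting only patients known to be progression-free would give about 48% and 58% at r = 20%. The protocol counts patients who did not progress, so the text does not set out that reading.
- *The start date matters materially.* The gap is a matter of days.
- *The 14-day window changes PFS broadly.* Resected patients have no further progression imaging, so after surgery it mainly affects deaths and incidental scans.

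**Conclusion.** The conflict over 3-month PFS is real and is in the current text of both documents. The crude formula in Protocol 10.6 is wrong as written for a trial in which resection censors PFS, and it does not fit the protocol's own plan in 10.1. On its literal reading it overstates the rate by about 2.6 to 3.6 points at 20% assigned censoring and about 5 to 7 points at 40%, under exponential PFS with the quoted medians and noninformative censoring. If nobody is censored before 3 months there is no difference. The documents do not say how many resections will come that early.

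The start date and the 14-day window are further real differences, the first negligible and the second narrow. Early death without a scan is an ambiguity to clear up. The flow chart in SAP Appendix 1 is not shown, so its order of precedence among the censoring rules could not be checked.

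Severity is moderate. A reader might infer that the trial's main result is at risk; it is not, because the primary biomarker analysis and the sample size do not use PFS.

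**What to change.** 1. In Protocol 10.6, replace the crude 3-month formula with the Kaplan-Meier 3-month rate and its 95% CI, in line with 10.1 and SAP 5.3.5.
2. Use first dose as the single start date in both documents, and keep one definition of enrolled.
3. State in 10.6 that death before any postbaseline scan is an event unless it falls after 2 scan intervals, as in the SAP.
4. Before the final database lock, adopt one censoring rule for new anticancer therapy and surgery alike in both documents, or state that SAP Table JGDM.5.1 supersedes 10.6. Removing the 14 days for surgery alone would not do: it leaves the conflict for other new therapy and censors post-surgical deaths that the SAP now counts as events.

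The cost is wording in the protocol and SAP. No new data, visits or patients are needed.
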